- Patients who meet the above criteria who have been prescribed CPAP or dental device but are adherent to treatment will be enrolled in the study provided that: a) they are willing to use the Wave device instead of their CPAP or dental device for the duration of the study, and b) they do not have severe OSA defined as an AHI > 30 events/hr in their clinical sleep study.

B. Key Exclusion Criteria

- Incapable of giving informed consent
- Under the age of 18
- Active titration of medication
- Pregnancy, lactation (will be screened with urine pregnancy test)
- Self-reported Substance abuse (current)
- Excessive alcohol consumption
 - Excessive alcohol use is defined as:
 - More than 3 glasses of wine a day
 - More than 3 beers a day
 - More than 60 mL of hard liquor a day
- Use of home oxygen
- Presence of severe daytime sleepiness defined as an Epworth sleepiness scale score ≥ 16 or a prior history of falling asleep while driving
- Presence of cardiac pacemaker or automatic implantable cardioverter-defibrillator (AICD).
- Unstable medical problem such as uncontrolled hypertension.
- Body Mass Index (BMI) $>45 \text{ kg/m}^2$
- Any other clinically significant condition that, in the opinion of the investigators, might put the subject at risk of harm during the study or might adversely affect the interpretation of the study data.

2. Screening Procedures

A screening visit will be scheduled to determine eligibility. A separate informed consent for the purpose of screening potential candidates will be obtained. Female patients of childbearing potential will be required to have a negative pregnancy test result at screening.

After their study participation has ended, those with an AHI ≥ 5 /hour based on the HSAT will be referred to their primary care physician or the sleep medicine clinic for treatment discussion using established therapies

3. Vulnerable Populations

- Children, fetuses, neonates, or prisoners are not included in this research study.

4. Populations vulnerable to undue influence or coercion

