- Participant signatures will be obtained using a typed name. Upon completion of the consent encounter, participants will be provided with a copy of the consent document by printing a pdf copy of the consent form.
- During the in-person consent process, consent will be obtained by a member of the study team. For self-initiated consent, contact information will be provided (email and phone) for prospective participants to contact a member of the study team with questions, prior to consent.

- After the screening consent has been signed, female patients of childbearing potential will be required to have a negative pregnancy test result.
- During this visit, the following will also be obtained:
 - a. Sleep Questionnaire and Medical History
 - b. Medication list
 - c. Body Mass Index, neck circumference (NC), blood pressure (BP), resting pulse oximetry, pulse rate
 - d. Collect results of the previous clinical sleep study
 - e. CPAP adherence, if applicable
 - f. Epworth Sleepiness Scale (ESS) score
 - g. Instructions on how to use the HSAT equipment at home for one night to obtain the baseline research HSAT study. Those with technically inadequate HSAT will have the study repeated.
- The following are the reasons why subjects may not proceed with the study after screening:
 - a) No POSA or POSA with APOC III based on the previous clinical sleep study.
 - b) No POSA or POSA with APOC III based on the baseline research HSAT study.
 - c) Meets one of the exclusion criteria.
 - d) Does not meet inclusion criteria.
- **Expected visit length: 60 minutes**
- Participants will be requested to return the HSAT device either in-person or via mail in a pre-paid envelope.

Visit 2

- Those who remain eligible will then sign a separate informed consent for the remainder of the study. REDCap will not be used for the consent process to the main study. The following will be obtained during this visit:
 - a. FOSQ
 - b. Assessment of sleep quality: VAS and Questionnaire
 - c. Actigraphy for duration of the study
 - d. Medications changes
- Participants will be given instructions on how to use Wave 4.3 mattress support at home and a phone number to call for the research coordinator for questions. The mattress support will be delivered at the subject's home by professional staff of the sponsor (Hill-Rom) in the presence of the research coordinator or investigator.
- **Expected visit length: 30 minutes**

Visit 3.

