- This will occur on the 14th day of sleeping with the mattress support (that is, after night 13). The purpose of this visit is to provide the HSAT device to be used while sleeping with the mattress support.
- Medication changes
- **Expected visit length: 20 minutes**

Visit 4.

- Return HSAT equipment.
- The following will be obtained during this visit:
 - a. ESS
 - b. FOSQ
 - c. Assessment of sleep quality: VAS and Questionnaire
 - d. Medication changes
- **Expected visit length: 30 minutes**
- It may be necessary to repeat the home sleep study for another night if data after sleeping with the Wave mattress support is not adequate.

Phone Calls: Phone calls will be made by an investigator or research staff to answer any questions that participants may have (will occur between Visits 2 and 3): after the second night (third day) and seventh night of sleeping on the Wave 4.3 surface.

Mattress support pick-up: The mattress support will be picked up by professional staff of the sponsor (Hill-Rom) in the presence of the research coordinator or investigator at a mutually agreed time.

Visit Schedule

Procedures	Visit #			
	1	2	3	4
Screening consent		x		
Study consent			x	
Pregnancy test, if applicable		x		
Clinical Sleep Study Results*	x			
CPAP adherence, if applicable	x			
Sleep Questionnaire and Medical History	x			
Medication list	x			
Medication changes		x	x	x
Height and weight	x			
Neck Circumference	x			
BP, Pulse rate, SpO ₂	x			
Provide HSAT Equipment	x	x		
ESS	x		x	
FOSQ	x	x		

Sleep quality	X	X
Wave instructions	X	
Actigraphy**	X	X X
Sleep diary**	X	X X

BP= blood pressure

SpO₂= oxygen saturation by pulse oximetry

HSAT= home sleep apnea test

ESS= Epworth Sleepiness Scale

FOSQ= Functional Outcomes of Sleep Questionnaire

VAS= Visual Analog Scale

*Clinical sleep study is completed per standard clinical care.

** Done while sleeping with Wave Mattress support for 14 days

D. Detailed Procedures

1. Clinical Sleep Study:

Subjects will undergo diagnostic sleep study according to the evaluation of their physician. This is the sleep study performed within the context of usual clinical care that will determine whether subjects meet the criteria for POSA.

2. OSU Sleep Questionnaire and Medical History (15 minutes)

Sleep Questionnaire (Visit 1 only; No need to complete if previously completed the OSU Sleep Disorders Center Questionnaire in sleep clinic)

3. Medication List (5 minutes)

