This research will be performed under a fully executed agreement between The Ohio State University and Hill-Rom (see attachment).

VIII. Data Safety Monitoring Plan

The risks involved with sleeping with the Wave mattress support, completion of questionnaires, HSAT, and actigraphy are minimal.

This study will be monitored to ensure participant safety and data integrity. The monitoring for this study will be conducted by the Principal Investigator and the study team. The information that will be evaluated will be the incidence and severity of adverse reactions related to the study procedures, enrollment and efficiency of data capturing. The adverse events will be assessed on a case by case basis at the time the study team is aware of the event.

Overall study monitoring will take place on an ongoing basis with study review meetings taking place at least every 4 months. In the event the side effects suggest the risk outweighs the benefit, the study will be stopped and the IRB notified in order to evaluate possible solutions to the risk problem.

VI. Bibliography

2. Strollo PJ, Jr., Rogers RM. Obstructive sleep apnea. *N Engl J Med* 1996;334:99-104.
3. Flemons WW. Clinical practice. Obstructive sleep apnea. *N Engl J Med* 2002;347:498-504.
5. Kuna ST, Gurubhagavatula I, Maislin G, et al. Noninferiority of functional outcome in ambulatory management of obstructive sleep apnea. *Am J Respir Crit Care Med*;183:1238-44.
8. George CF. Reduction in motor vehicle collisions following treatment of sleep apnoea with nasal CPAP. *Thorax* 2001;56:508-12.
10. Somers VK. Sleep--a new cardiovascular frontier. *N Engl J Med* 2005;353:2070-3.

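### Participants who give up an adherent CPAP or dental-device treatment get no scheduled sleepiness question until after the device nights; one scripted question at the two planned calls would close the gap.

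*Combined protocol and SAP*

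**What the plan says.** **Who switches.** Under Key Inclusion Criteria (III.B.1.A), patients adherent to CPAP or a dental device may enrol if "they are willing to use the Wave device instead of their CPAP or dental device for the duration of the study" and their clinical AHI is not above 30. Wave is used at home for two consecutive weeks (III.C).

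**Entry check.** Key Exclusion Criteria (III.B.1.B) rule out "Presence of severe daytime sleepiness defined as an Epworth sleepiness scale score ≥ 16 or a prior history of falling asleep while driving". They also let investigators exclude anyone with a condition that "might put the subject at risk of harm during the study". The score is collected at Visit 1 ("f. Epworth Sleepiness Scale (ESS) score"), with nothing said about being on or off treatment at the time.

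**After the switch.** Participants receive "a phone number to call for the research coordinator for questions". On the scheduled calls the plan says "Phone calls will be made by an investigator or research staff to answer any questions that participants may have", and it times them "after the second night (third day) and seventh night of sleeping on the Wave 4.3 surface". In the visit text, Visit 3 (after night 13) covers the HSAT device and medication changes. The ESS is next listed at Visit 4. The visit table is broken in the available copy, so this timing is taken from the visit text.

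**Monitoring.** Section VIII says "The risks involved with sleeping with the Wave mattress support, completion of questionnaires, HSAT, and actigraphy are minimal". It provides for case-by-case assessment of adverse events once the team knows of them, review meetings at least every 4 months, and a study-level stop if risk outweighs benefit. Section V requires adverse events to be recorded from consent to the completion visit. Section VI(a) says a subject may withdraw or be withdrawn at any time.

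**The concern.** The protocol recognises the hazard. Its Background says OSA causes daytime sleepiness and is associated with motor vehicle crashes, and it excludes severe sleepiness and prior falling asleep while driving. For a patient well controlled on CPAP, however, the entry score probably describes the treated state. The patient then moves to a device whose effect on AHI is what the study sets out to measure. If Wave works poorly for that person, sleepiness may return during the device nights, and no one is scheduled to ask about it while there is still time to act.

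What is at stake is a preventable individual harm, chiefly drowsy driving. There is also a smaller analytic point. Participants who leave because sleepiness returns are likely to be poor responders, so losing them without report would flatter the paired comparison.

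**Working it through.** **1. When each safeguard acts.**

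| Safeguard | Where | Prompts detection of new sleepiness after the switch? |
|---|---|---|
| AHI above 30 barred for adherent users | III.B.1.A | No; acts before the switch |
| APOC I/II on the clinical study; no POSA or APOC III on the baseline research HSAT stops entry | III.B.1.A; Visit 1 | No; acts before the switch |
| ESS and driving-history exclusion; investigator discretion | III.B.1.B | No; acts before the switch |
| Remote sensors | III.D.9 | No; they report on the device |
| Nightly sleep diary | III.C | Not as described; no review during the device nights is stated |
| Coordinator phone number | Visit 2 | Only if the participant calls |
| Calls after nights 2 and 7 | Phone Calls | Only if the participant raises it |
| AE recording, case-by-case review | V; VIII | Only once the team is aware |
| Withdrawal right | VI(a) | Only once someone acts; no criterion given |
| Review meetings at least every 4 months | VIII | No; one participant's study lasts up to 4 weeks |

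**2. Which contacts leave time to act.** Device nights remaining out of 14:
- after the first call: 14 − 2 = 12
- after the second call: 14 − 7 = 7
- at Visit 3: 14 − 13 = 1

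The two calls are therefore the useful contacts. The counts cover device nights only. Treatment is replaced for the duration of the study, so the time off it may be longer.

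**3. What exits would cost in power.** Inputs from IV, Sample size: SD of paired differences 11.4, reduction of 6, one-sided alpha 0.05, 24 evaluable, 40 enrolled, 20% screen failure and 20% loss.

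The plan's figure first. Noncentrality is √n × 6/11.4 on n − 1 degrees of freedom. At n = 24 it is √24 × 0.526 = 2.58, the critical t is 1.714, and power is 80.4%. The stated 24 reproduces. Enrolment: 24/0.60 = 40, that is 40 − 8 − 8 = 24, so the allowance is 8 losses.

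Exits on top of those 8:

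| Extra exits | n | Power, single look |
|---|---|---|
| 0 | 24 | 80.4% |
| 1 | 23 | 78.8% |
| 2 | 22 | 77.1% |
| 3 | 21 | 75.3% |
| 4 | 20 | 73.4% |

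These figures ignore the interim look. A simulation with the planned boundaries (interim at 12 patients, efficacy p < 0.006, futility p > 0.37, final p < 0.048) gives about 80.2% at n = 24 and 73.0% at n = 20 if the non-binding futility rule is not applied. If it is applied, the figures are 78.7% and about 72.5%. The cost of exits is of the same order either way. Exits that fall within the 8 planned losses cost no power relative to plan.

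**The case against.** **These patients are not left untreated.** A reader might infer two weeks without therapy. The documents do not support that. Patients change to a device intended to treat positional OSA, and APOC I/II selection on the clinical study, with a further check on the baseline HSAT, picks those whose disease should respond to positional treatment. This objection stands. What remains is that Wave's effect is unproven, so an individual may respond poorly.

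**Section VIII does not show that the risk is undisclosed.** A reader might infer from its list that participants are not told about the risk of stopping treatment. The consent pages are not in the available file, and VI(a) has staff answer questions on risks and alternatives. Adding a line to the list would be largely editorial. Disclosure, even if complete, would still not add a check during the device nights.

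**New sleepiness would already be recordable.** Section V counts events resulting from protocol procedures and protocol treatment, and replacing CPAP can reasonably be read as part of that. This is fair, but recording depends on the team learning of the event.

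**The size is unknown.** An enrolled patient with an ESS of 15 needs only one more point to reach the cut-off, and a reader might take that as a measure of the problem. It is a boundary case, equally true of any participant scoring 15, adherent or not, and says nothing about frequency.

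**Scoring the ESS at the calls would have a price.** The ESS is a study outcome compared before and after. Extra scoring in one subgroup, with action attached, would make its measurement unequal and could colour the Visit 4 answers. Nothing in the documents supports scoring it after two nights. This objection stands and shapes the fix.

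**Conclusion.** The gap is real but narrow. Between Visit 1 and Visit 4 the visit text schedules no sleepiness question for participants who have given up an adherent treatment, and every safeguard that operates after the switch waits for the participant or the team to notice a problem. Two contacts that could close the gap are already planned.

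The conclusion rests on two readings: that the Visit 1 ESS is usually taken while the patient is still on treatment, which the plan neither requires nor rules out, and that the visit text gives the ESS timing correctly. The number of patients affected cannot be derived, because no adherent share, cap or ESS distribution is given. The documents do not support a claim that harm is likely or common, or that the study is unsafe as designed. The point is one to consider: a low-cost improvement in a short feasibility study.

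**What to change.** Amend the Phone Calls paragraph in III.C, with a matching sentence in section VIII. For participants who stop an adherent CPAP or dental-device treatment:

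1. At each of the two existing calls, ask one scripted question: has there been new or worse daytime sleepiness, including dozing while driving?
2. If yes, an investigator contacts the participant the same day, advises on driving, and decides whether to resume CPAP or the dental device under the existing withdrawal authority.
3. Report the number of such exits and their reasons with the primary result.

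Do not score the ESS at the calls.

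**Cost.** A short amendment and a few minutes per call, for this subgroup only. No new visit, staff, committee or HSAT is needed. An exit before night 14 may lose a primary endpoint. Only exits beyond the 8 planned losses reduce power, by the amounts shown in the table above.
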